#### 5.7.6.5 *Additional Tabulations*

Pain freedom, pain relief, freedom from MBS, and functional disability score will be tabulated by treatment group at each post-dose time point. Success for each of these endpoints will be tabulated using the mITT subjects.

Freedom from nausea, freedom from phonophobia, freedom from photophobia, and functional disability scale response will be tabulated by treatment group at each post-dose time point. The tabulation will include: the total number of subjects reporting each of the above symptoms at baseline, success as the percentage of the total number of subjects reporting the symptoms at baseline, and the number of subjects that reported the symptom but with missing data at the post-dose time point as a percentage of the number reporting the symptom at baseline.

#### 5.7.6.6 *Sheehan-Suicidality Tracking Scale (S-STS)*

The S-STS is a prospective, self-reported rating scale that contains 16 questions to track both treatment-emergent suicidal ideation and behaviors. In the event the subject is unavailable, the S-STS clinician-administered rating scale will be completed that contains 6 yes/no questions.

Self-reported S-STS scores are calculated as follows:

- Ideation subscale score: Sum of scores (0 – 4) for Questions 2 – 11
- Behavior subscale score: Sum of scores (0 – 4) for Questions 1a, (highest of 12 or any row of 16), (highest of 14 or any row of 15), 17, and 20
- Total score: Sum of the ideation and behavior subscale scores

The self-reported S-STS ideation subscale, behavior subscale, and total score will be summarized at baseline and the change from baseline (i.e., <-1, -1, no change, 1, >1) will be summarized at the end of treatment visit.

#### 5.7.6.7 *Pain Freedom to 8 Hours Post-Dose*

Pain freedom over time up to 8 hours will be analyzed using Kaplan-Meier methods. Kaplan-Meier estimates will be tabulated using the following time periods (0 through 30 minutes, > 30 through 60 minutes, > 60 through 90 minutes, > 90 through 120 minutes, >120 minutes through 180 minutes, >180 minutes though 240 minutes, >240 minutes though 360 minutes, >360 minutes though 495 minutes, and > 495 minutes). For each time period, the number of subjects at risk, with an event (pain freedom), censored, and survival probability estimate (with 95% CI), will be presented by treatment group. Subjects who fail to reach no pain by 495 minutes, will be censored at 495 minutes. Additionally, subjects who take rescue medication prior to 495 minutes will be censored at the date/time associated with their rescue medication. Note that the probability of survival corresponds to the probability of NOT having pain freedom. Survival estimates are calculated using the Kaplan-Meier product-limit method and median survival (time to pain freedom), and will be presented along with 95% CIs calculated using the method of Brookmeyer and Crowley.

To support the analysis, a Kaplan-Meier plot, with time in minutes on the x-axis and probability of survival on the y-axis, will be presented by treatment group. The number at risk at each time point (0, 15, 30, 45, 60, 90, 120, 180, 240, 360, and 495) minutes will be presented below the figure. In this analysis, being at risk corresponds to not yet having achieved pain freedom; therefore, the subject is still “at risk” of having pain freedom. Once a subject has pain freedom or is censored, then the subject is no longer in the risk pool. If a subject has missing data at an earlier time point, then the time point with missing data is not considered. The subject is still considered at risk of failure at a future time point if data are available. Subjects are censored as described above.

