⁹ Patients will be randomized in the IWRS system at the Baseline Visit (Randomization Day 01)

¹⁰ Patient should be instructed that the dose should be taken once the migraine attack reaches moderate or severe pain.

¹¹ Site staff to review and confirm entries with patients and confirm all data points are transferred to the system and reset eDiary for future patient use, PRIOR to the patient leaving the clinic.

¹² ± Windows for timeframe around efficacy assessments (15, 30, 45, 60, 90 min, 2, 3, 4, 6, 8, 24 and 48 hours) will be automated and captured in the eDiary.

¹³ These scales will be captured in the eDiary. Patients will also be asked about their most bothersome symptom at the time of reporting and treating a qualifying migraine.

¹⁴ Paper source document will be used to capture Migraine History. Patients will also be asked about their typical most bothersome symptom when having a migraine.

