#### **5.7.6.2 Pain Relief at 30, 60 and 90 Minutes Post-Dose**

Pain relief at 30, 60, and 90 minutes post-dose will be assessed by tabulating the number of mITT subjects that report a pain level of none or mild (responses of 0 or 1 on the 4-point Likert scale) at the specified post-dose time point by treatment group. Subjects with missing data at the specified post-dose time point will be imputed as failures (NC=F).

First, the data will be evaluated at each time point, using the first analysis methods described in Section 5.7.3.1.

Pain relief over time up to 2 hours will be analyzed using Kaplan-Meier methods. Kaplan-Meier estimates will be tabulated using the following time periods (0 through 30 minutes, > 30 through 60 minutes, > 60 through 90 minutes, > 90 through 135 minutes, and >135 minutes). For each time period, the number of subjects at risk, with an event (pain relief), censored, and survival probability estimate (with 95% CI), will be presented by treatment group. Subjects who never reach mild or no pain by 135 minutes, will be censored at 136 minutes. Additionally, subjects who take rescue medication prior to 135 minutes will be censored at the date/time associated with their rescue medication. Note that the probability of survival corresponds to the probability of NOT having pain relief. Survival estimates are calculated using the Kaplan-Meier product-limit method and median survival (time to pain relief), and will be presented along with 95% CIs calculated using the method of Brookmeyer and Crowley.

To support the analysis, a Kaplan-Meier plot, with time in minutes on the x-axis and probability of survival on the y-axis, will be presented by treatment group. The number at risk at each time point (0, 15, 30, 45, 60, 90, and 135) minutes will be presented below the figure. In this analysis, being at risk corresponds to not yet having had pain relief; therefore, the subject is still “at risk” of having pain relief. Once a subject has pain relief or is censored, then the subject is no longer in the risk pool. If a subject has missing data at an earlier time point, then the time point with missing data is not considered. The subject is still considered at risk of failure at a future time point if data are available. Subjects are censored as described above.

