## **2.2 Time to First Report of Absence of Various Symptoms**

For each of the following variables, two sets of Kaplan-Meier plots and tables were created:

- Time to First Report of Absence of Most Bothersome Symptom
- Time to First Report of Absence of Nausea
- Time to First Report of Absence of Photophobia
- Time to First Report of Absence of Phonophobia
- Time to First Report of Return to Normal Functioning

The first set of plots and tables was similar to those created for the time to rescue medication (using actual time). For the second set of plots, nominal (planned time point) as opposed to actual time was used for clinical event times. Censoring was measured using actual time as in all previous plots.

For both sets of analyses, the analysis population for MBS and functional disability was the set of mITT subjects. The analysis population for nausea, phonophobia, and photophobia was the subset of mITT subjects that reported the symptom as present at the onset of their study migraine. The y-axis for all plots represents the probability of the occurrence of the event of interest, and therefore are increasing from left to right.

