### **2.2.1 Kaplan-Meier Plots and Tables: Actual Time for Event of Interest**

The first set of K-M plots and tables were created using actual time of censoring and actual time for the clinical event of interest. Subjects were censored at the actual time of their first use of rescue medication or last reported data point if lost to follow-up. Subjects who did not have the clinical event of interest by 8 hours post dose were censored at 496 minutes (480 minutes + 15 minute window + 1 minute).

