### **2.2.2 Kaplan-Meier Plots and Tables: Nominal Time for Event of Interest**

The second set of K-M plots and tables were created for the above variables with nominal time (planned time of collection, e.g., 2 hours, 3 hours, etc.) used for clinical events of interest and actual time used for censoring events. Subjects were censored at the actual time of their first use of rescue medication or last reported data point if lost to follow-up. Subjects who did not have the clinical event of interest by 8 hours post dose were censored at 496 minutes (480 minutes + 15 minute window + 1 minute).

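### The time-to-pain-freedom table in SAP 5.7.6.7 appears to split the 2-hour diary assessment at 120 minutes, unlike its companion table, and Appendix 4 section 2.2.2 can reverse the order of event and rescue

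*SAP*

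**What the plan says.** **Pain freedom (SAP 5.7.6.7).** The rows include "> 90 through 120 minutes, >120 minutes through 180 minutes" and close with ">360 minutes though 495 minutes, and > 495 minutes". The number at risk is shown at 120, 180, 240, 360 and 495 minutes, among other times. Subjects with no event are censored at 495. The tabulated quantity is the probability of not having reached pain freedom.

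**Pain relief (SAP 5.7.6.2).** The last rows are "> 90 through 135 minutes, and >135 minutes", the final at-risk count is at 135, and subjects with no event are censored at 136.

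**Windows.** Appendix 4 section 2.2.1 builds its censoring time as "480 minutes + 15 minute window + 1 minute". This is the only place where a width is written out, and it is for 8 hours. Footnote 12 to the protocol's Schedule of Assessments (4.3) refers to plus-or-minus "Windows for timeframe around efficacy assessments (15, 30, 45, 60, 90 min, 2, 3, 4, 6, 8, 24 and 48 hours" and gives no widths. SAP Table 6 identifies the 2-hour efficacy assessment as the one captured in the eDiary.

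**Clock.** Neither 5.7.6.2 nor 5.7.6.7 says whether events are timed by diary stamp or by planned time point. Appendix 4 section 2.2 says "Censoring was measured using actual time as in all previous plots". Section 2.2.2 then has nominal time "used for clinical events of interest and actual time used for censoring events".

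**Status.** SAP Appendix 1 flags both Kaplan-Meier tables (14.2.3.8.3 and 14.2.3.9.1) as topline. SAP 5.7.6 makes their p-values descriptive. The Appendix 4 analyses are post hoc.

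**The concern.** Two topline tables cut the same diary entry differently. A 2-hour entry stamped between minutes 121 and 135 lies inside the row ending at 135 in the pain-relief table. In the pain-freedom table it lies in the row that otherwise holds the 3-hour entries. Anyone reading the two tables together, or taking the 120-minute row as pain freedom through the 2-hour assessment, would see less pain freedom than was reported at that assessment.

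The Appendix 4 issue is different in kind. If an event is moved to its planned time and rescue is left at its actual time, their order can change. SAP 2.3 (the RM=F rule) and SAP 5.7.1 treat any evaluation that coincides with or follows rescue as a failure. Section 2.2.2, followed literally, could count such an evaluation as an event.

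**Working it through.** **1. The plan's own limits.** 480 + 15 = 495 (last bounded row of 5.7.6.7). 480 + 15 + 1 = 496 (Appendix 4 censoring). 120 + 15 = 135 and 135 + 1 = 136 (last bounded row and censoring time of 5.7.6.2). All reproduce. The 15-minute width at 2 hours is inferred from the 135 limit; no text states it. One further mismatch: 5.7.6.7 censors at 495, so its row beyond 495 can hold no one.

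**2. Which clock.** On nominal time, 2-hour and 8-hour events would sit at exactly 120 and 480, and limits of 135 and 495 would have no purpose. Appendix 4 also introduces nominal event times as a contrast to actual time. Both facts point to actual time in 5.7.6.7, but the section does not say so.

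**3. Effect on the row.** Assume no censoring before minute 135. Let p be the share pain free at least once through the 2-hour entry, g the share of p first reported at that entry, and f the share of those reports stamped after minute 120. Then

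S(120) − S(135) = p × g × f,

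and cumulative pain freedom at 120 is p × (1 − g × f).

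For p, take the Phase 2b 2-hour rates in protocol 1.4.2, 31.4% and 15.3%, as an illustration only: those are rates of status at 2 hours, not cumulative first reports. The values of g and f are assumptions.

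| g | f | Active, pain free by 120 min | Placebo | Difference (points) |
|---|---|---|---|---|
| any | 0 | 31.4% | 15.3% | 16.1 |
| 25% | 50% | 27.5% | 13.4% | 14.1 |
| 25% | 100% | 23.6% | 11.5% | 12.1 |
| 50% | 50% | 23.6% | 11.5% | 12.1 |
| 50% | 100% | 15.7% | 7.7% | 8.05 |

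Example: 0.314 × 0.5 × 0.5 = 0.0785, so S(120) = 0.686 + 0.0785 = 0.764 for active; 0.153 × 0.5 × 0.5 = 0.038, so S(120) = 0.885 for placebo. With the row ended at 135, the table would show 0.686 and 0.847.

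A simulation with stamps uniform over minutes 105 to 135 and g = 50% agreed. S(120) against S(135) was 0.758 against 0.682 for active, and 0.887 against 0.849 for placebo.

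**4. Appendix 4 section 2.2.2, with illustrative minutes.**
- Rescue at 182 and a symptom-free 3-hour entry at 188: the event is placed at 180, before rescue. Under the RM=F rule this evaluation is a failure.
- Symptom-free 3-hour entry at 170 and rescue at 175: the event is placed at 180, after censoring at 175, so a report made before rescue is lost.
- Entry at 170 with the symptom still present and rescue at 175: the subject was assessed at the 3-hour point but has left the risk set before 180, so that denominator is too small.

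**The case against.** The strongest reply is that both tables follow one convention: interior rows are cut at nominal minutes, and 15 minutes are added only at the end of the analysis. On that reading, 120 minutes is the horizon in 5.7.6.2 and an interior point in 5.7.6.7. This is a fair account of the row limits, since 5.7.6.2 also leaves its cuts at 30, 60 and 90 minutes without a window. It explains the difference but does not remove it: the same diary slot is whole in one topline table and split in the other.

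Several further objections stand.
- S(120) correctly estimates the probability of no pain-free report by 120 actual minutes. The rows are labelled in minutes, not as assessments.
- The plus-or-minus windows allow entries before minute 120, and those do not move. On nominal time none move.
- Pain freedom by diary slot is already reported: the co-primary table (14.2.1.2, topline) and the tabulation at every time point (14.2.3.8.7).
- The Appendix 4 rule covers other symptoms and functioning, not pain freedom. Each nominal-time analysis has an actual-time counterpart, and the text does not say how ties of order are settled. The reversal follows from applying the rule as written.

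A reader might infer that the topline 2-hour pain-freedom estimate is biased low, or that this row ought to agree with the co-primary result. The documents support neither. The co-primary endpoint is status at the 2-hour slot, with missing data and rescue counted as failure. The Kaplan-Meier analysis counts the first pain-free report at any earlier time, skips missing time points and censors at rescue. The two would differ even with a limit at 135.

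**Conclusion.** The point holds as a minor inconsistency of display, on two conditions: event times in 5.7.6.7 are actual times, and some 2-hour entries are stamped after minute 120. The row at 120 then shows a higher probability of not being pain free, and lower cumulative pain freedom, than applies through the 2-hour assessment.

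No size can be taken from the documents. Under the illustrative assumptions the shift runs from 0 to 15.7 points for active and from 0 to 7.7 points for placebo. Zero is a real possibility, so none of these figures should be quoted as an expected error.

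The Kaplan-Meier curve, the median time and the co-primary analysis do not change. The interior rows at other time points have the same nominal cut, but their window widths are not given. A full 15 minutes either side could not apply without overlap to assessments only 15 minutes apart, so that width should not be assumed throughout.

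The Appendix 4 rule is a separate small defect: as written it can contradict the plan's own handling of rescue, in post-hoc analyses only.

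**What to change.** **SAP 5.7.6.7 and 5.7.6.2.** State whether events are timed by diary stamp or by planned time point. Then do one of the following:
- tabulate events and numbers at risk by nominal time point; or
- end every row, including those at 30, 60 and 90 minutes, at the upper limit of the eDiary window for that assessment, and show numbers at risk at the same times. For 2 hours that limit is 135; take the others from the eDiary specification.

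Use one censoring convention, so that the row beyond 495 is either reachable or dropped.

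**Appendix 4 section 2.2.2.** Decide on actual times whether the event or rescue came first. Then place events at nominal time, and keep subjects who were assessed without an event in the risk set for that time point.

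**Cost.** Minor reprogramming of exploratory and post-hoc tables and figures, plus a sentence or footnote in each section. No confirmatory result changes.

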**Summary of Changes**

V1.0: Original

V2.0: Added Appendices 4 and 5 to describe post-hoc supportive analyses

**Author:** PPD

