**RM=F: Rescue Medication = Failure.**

Subjects that take rescue medication before, or at, the time of the event of interest are classified as failures. If the time of rescue medication is missing, all events on or after the date of rescue medication are classified as failures.

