### **5.7.1 Rescue Medication**

Subjects who take rescue medication as recorded on the CRF or any medication used for headaches as recorded anywhere on the CRF or eDiary will be considered as failures for any efficacy evaluations that are coincident or follow the administration of the rescue medication/other headache medication. If the time of rescue medication is missing, subjects will be considered as failures for any efficacy evaluations are on or after the date of administration of the rescue medication/other headache medication.

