### **5.7.6 Exploratory Efficacy Endpoints**

Any p-values presented for exploratory efficacy endpoints are for descriptive purposes only.

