14.2.3.3.2	Pain Relief at 2 Hours Post Dose: Secondary Analysis	mITT Subjects	Y

Table Number	Title	Population	Topline
14.2.3.4.1	Freedom from Nausea at 2 Hours Post Dose in Subjects who Reported Nausea at Study Migraine Onset: Observed Data	mITT Subjects	
14.2.3.4.2	Freedom from Nausea at 2 Hours Post Dose in Subjects who Reported Nausea at Study Migraine Onset: Secondary Analysis	mITT Subjects	Y
14.2.3.5	Rescue Medication within 24 Hours Post Dose: Secondary Analysis	mITT Subjects	
14.2.3.6.1	Functional Disability Scale at 2 Hours Post Dose: Observed Data	mITT Subjects	
14.2.3.6.2	Functional Disability Scale at 2 Hours Post Dose: Secondary Analysis	mITT Subjects	
14.2.3.7.1	Sustained Pain Freedom from 2 to 24 Hours Post Dose: Secondary Analysis	mITT Subjects	
14.2.3.7.2	Sustained Pain Relief from 2 to 24 Hours Post Dose: Secondary Analysis	mITT Subjects	
14.2.3.7.3	Sustained Pain Freedom from 2 to 48 Hours Post Dose: Secondary Analysis	mITT Subjects	
14.2.3.7.4	Sustained Pain Relief from 2 to 48 Hours Post Dose: Secondary Analysis	mITT Subjects	
14.2.3.7.5	Pain Relapse from 2 to 48 Hours Post Dose: Secondary Analysis	mITT Subjects	
14.2.3.8.1	Functional Disability Scale at 24 Hours Post Dose: Exploratory Analysis	mITT Subjects	
14.2.3.8.2	Pain Relief at 30, 60, and 90 Minutes Post Dose: Exploratory Analysis	mITT Subjects	
14.2.3.8.3	Kaplan-Meier Time to Pain Relief: Exploratory Analysis	mITT Subjects	Y
14.2.3.8.4	Median Time to Pain Relief	mITT Subjects	Y
14.2.3.8.5	Preference of Medication at 24 Hours Post Dose: Exploratory Analysis	mITT Subjects	
14.2.3.8.6.1	Migraine Quality of Life Questionnaire at 24 Hours Post Dose: Continuous Exploratory Analysis	mITT Subjects	
14.2.3.8.6.2	Migraine Quality of Life Questionnaire at 24 Hours Post Dose: Frequency Exploratory Analysis	mITT Subjects	
14.2.3.8.7	Pain Freedom at Every Timepoint Post Dose: Exploratory Analysis	mITT Subjects	
14.2.3.8.8	Pain Relief at Every Timepoint Post Dose: Exploratory Analysis	mITT Subjects	
14.2.3.8.9	Freedom from Most Bothersome Symptom at Every Timepoint Post Dose: Exploratory Analysis	mITT Subjects	
14.2.3.8.9.1	Freedom from Photophobia at Every Timepoint Post Dose: Exploratory Analysis	mITT Subjects	
14.2.3.8.9.2	Freedom from Phonophobia at Every Timepoint Post Dose: Exploratory Analysis	mITT Subjects	
14.2.3.8.9.3	Freedom from Nausea at Every Timepoint Post Dose: Exploratory Analysis	mITT Subjects	

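### Measured against the SAP's own rescue-is-failure rule, the 8-hour Kaplan-Meier curves that censor at rescue overstate response in each arm; a minor point, confined to exploratory and post hoc output

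*SAP*

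**What the plan says.** SAP 5.7.6.7 plans Kaplan-Meier estimates of time to pain freedom to 495 minutes, in which "subjects who take rescue medication prior to 495 minutes will be censored at the date/time associated with their rescue medication". On reading the output it adds: "Note that the probability of survival corresponds to the probability of NOT having pain freedom". The response a reader takes from the curve is therefore one minus the printed value. A median is also reported. SAP Appendix 1 marks the table, the median and the plot as topline.

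SAP Appendix 4, sections 2.2.1 and 2.2.2, censors at first rescue in the curves for first absence of the most bothersome symptom, nausea, photophobia and phonophobia, and for return to normal function. Those plots show the rising probability of response directly. Section 2.3 pools them with BHV3000-301.

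The general rule differs. Under RM=F in SAP 2.3, "Subjects that take rescue medication before, or at, the time of the event of interest are classified as failures". SAP 5.7.1 says that rescued subjects "will be considered as failures for any efficacy evaluations that are coincident or follow the administration of the rescue medication/other headache medication". Tables 1 to 3 contain no estimand for any of these time-to-event curves.

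On status, SAP 5.7.6 states "Any p-values presented for exploratory efficacy endpoints are for descriptive purposes only", and the Summary of Changes records "Added Appendices 4 and 5 to describe post-hoc supportive analyses".

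**The concern.** Kaplan-Meier lets those still at risk stand in for those censored. That is reasonable only if leaving the risk set says nothing about later response. Protocol 5.4.1 makes this implausible: rescue is permitted only after the 2-hour assessment, for patients without relief or whose pain has returned to moderate or severe. Those removed are mainly those doing badly.

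At stake is how topline output reads. In 5.7.6.7 the printed survival is too low, so the response it implies is too high; in Appendix 4 the plotted probability is itself too high. A median, where reached, can come too early, or can appear when fewer than half the arm responded.

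Two neighbouring analyses are not part of the point. Time to rescue (Appendix 4, section 2.1) has rescue as its event. Pain relief to 135 minutes (SAP 5.7.6.2) leaves little room for permitted rescue.

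**Working it through.** The plan gives no expected rate for these curves, so there is no figure of its own to reproduce.

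**Direction.** At each response time, with d responses among Y at risk, Kaplan-Meier adds S(t−)·d/Y, where S ignores rescue. Cumulative incidence with rescue as a competing event adds G(t−)·d/Y, where G is the proportion with neither response nor rescue. G is never above S, so one minus Kaplan-Meier is never below the rescue-as-failure response. It is strictly higher once any response follows a rescue. This needs no assumption about rates.

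**Inputs for size.** Protocol 1.4.2 (Phase 2b, 2 hours): pain free 31.4% vs 15.3%; mild or no pain 72.1% vs 51.2%.

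- Rimegepant: pain free f = 0.314; mild M = 0.721 − 0.314 = 0.407; non-relief N = 1 − 0.721 = 0.279.
- Placebo: f = 0.153; M = 0.512 − 0.153 = 0.359; N = 1 − 0.512 = 0.488.

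**Assumptions (not in the documents).** By 8 hours, pM = 60% of mild and pN = 20% of unrescued non-relief subjects become pain free. A share r of non-relief subjects is rescued before 3 hours. Rescue for recurrence is ignored.

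**Formulas.** Let E = M·pM + N(1−r)·pN.

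- Rescue as failure: f + E.
- One minus Kaplan-Meier: 1 − (1−f)·[1 − E/(M + N(1−r))].
- Hypothetical, no rescue available: f + M·pM + N·pN.

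**At r = 50%** (0.5 × 27.9% = 14.0% of the rimegepant arm; 0.5 × 48.8% = 24.4% of placebo):

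- Rimegepant: E = 0.2442 + 0.0279 = 0.2721. Rescue as failure 0.314 + 0.2721 = 58.6%. Kaplan-Meier 1 − 0.686 × (1 − 0.2721/0.5465) = 65.6%.
- Placebo: E = 0.2154 + 0.0488 = 0.2642. Rescue as failure 0.153 + 0.2642 = 41.7%. Kaplan-Meier 1 − 0.847 × (1 − 0.2642/0.603) = 52.4%.
- Hypothetical: 61.4% and 46.6%, so Kaplan-Meier is 4.2 and 5.8 points above that target too.

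**Varying the rescue share.** In the spread version the same shares are rescued evenly over the 3, 4, 6 and 8 hour readings, with per-reading rates 1 − (1−r)^¼ for rescue and 1 − (1−p)^¼ for response.

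| Share of non-relief rescued | Before 3 h, rimegepant: KM vs failure | Before 3 h, placebo | Spread, rimegepant | Spread, placebo |
|---|---|---|---|---|
| 30% | 63.7 vs 59.7 | 49.6 vs 43.7 | 62.9 vs 60.3 | 48.4 vs 44.7 |
| 50% | 65.6 vs 58.6 | 52.4 vs 41.7 | 64.1 vs 59.6 | 50.2 vs 43.4 |
| 70% | 67.9 vs 57.5 | 56.3 vs 39.8 | 65.9 vs 58.7 | 52.9 vs 41.8 |

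From unrounded values, the excess before 3 hours is 3.9 to 10.4 points on rimegepant and 5.9 to 16.5 on placebo; spread, it is 2.5 to 7.2 and 3.7 to 11.1.

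**Varying later response** (r = 50% before 3 hours; mild 40% to 80%, non-relief 10% to 30%). The excess over rescue as failure is 4.5 to 9.4 points on rimegepant and 6.8 to 14.6 on placebo. Over the hypothetical target it is 1.0 to 7.3 and 1.5 to 10.2; it would vanish if mild and non-relief subjects responded alike.

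**Between-arm difference** (rescue before 3 hours; shares are of non-relief subjects):

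| Rimegepant / placebo share | Kaplan-Meier | Rescue as failure |
|---|---|---|
| 50% / 50% | 13.1 | 16.9 |
| 70% / 50% | 15.5 | 15.8 |
| 70% / 30% | 18.3 | 13.8 |

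**The case against.** The best defence is that the correction can largely be read from the planned output. The 5.7.6.7 table also prints, by period and arm, the numbers at risk, with an event and censored. Cumulative events over the starting number approximate the rescue-as-failure response. The Appendix 4 tables are modelled on ones with the same columns. This stands as a partial mitigant: the distortion is not hidden, but the survival estimate, plot and median still carry it. SAP 5.7.6.5 also helps: "Pain freedom, pain relief, freedom from MBS, and functional disability score will be tabulated by treatment group at each post-dose time point", with 5.7.1 making rescued subjects failures there. But "Pain Freedom at Every Timepoint Post Dose: Exploratory Analysis" is not marked topline, and such tables give rates at a time point, not the incidence of first response.

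A second defence is that no rule is broken. Tables 1 to 3 cover the listed objectives, and time to pain freedom is not one. No response after rescue is counted as an event, which respects the letter of 5.7.1. That is fair. What remains is an unstated estimand and an estimator that does not deliver the rescue-as-failure quantity. SAP section 3 is redacted, so nothing is inferred from it; the estimand section is visible.

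Third, too high depends on the target. Against a treatment-policy target, which counts response after rescue, the sign can reverse. In the 50% illustration it does so if more than 6.95/13.95 = 50% of rescued rimegepant subjects, or 10.69/24.4 = 44% of rescued placebo subjects, become pain free by 8 hours. The SAP does not use that target for its pain or symptom response endpoints.

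**Conclusion.** The point holds as a minor one. Relative to rescue as failure, the 8-hour pain-freedom curve and the Appendix 4 first-response curves overstate cumulative response in each arm. That direction is algebraic. Overstatement against a hypothetical no-rescue target also requires that rescued subjects would have responded less often than those still at risk, which the rescue criteria make likely.

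The size is not known. About 2.5 to 10.4 points on rimegepant and 3.7 to 16.5 on placebo is the range over the assumed rescue shares and timings, for pain freedom only; no figure is offered for the Appendix 4 symptoms.

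A reader might infer three stronger things that the documents do not support:

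- That the censoring flatters the drug. The difference can shrink, hold or widen, and the widening case shown needs non-relief subjects on rimegepant to take rescue more than twice as often as those on placebo.
- That a spurious placebo median will be printed. It appears at a 50% share, only just when rescue is spread (50.2%), and not at a 30% share (49.6%, or 48.4% spread). At a 50% share before 3 hours it is also absent with 40% later response in mild subjects (38.9% to 45.8%).
- That confirmatory conclusions are at risk. The co-primary and fixed-sequence tests do not use these curves.

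**What to change.** In SAP 5.7.6.7 and Appendix 4, section 2.2:

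- State the estimand for each curve.
- Present the cumulative incidence of first response with rescue as a competing event (Aalen-Johansen), censoring early only for loss to follow-up. With no other early loss, this equals keeping rescued subjects as non-responders to 495 minutes (5.7.6.7) or 496 minutes (Appendix 4).
- Report a median only if that incidence reaches 50%.
- Keep the rescue-censored Kaplan-Meier curves only as a sensitivity analysis, labelled with the hypothetical estimand and the assumption that rescue is unrelated to later response.

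Gray's test for any between-arm p-value, and weighting by the pain score before rescue, are optional.

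No new data are needed. The cost is a change of estimator and a rerun of the Appendix 4 and pooled curves, which are mostly described in the past tense and appear already produced. Displayed response will be lower in both arms.
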